10.5 Reporting of SUSARs

A serious adverse reaction that is not expected according to the current IB and where the causality is assessed as "definitely", "probably" or "possibly", qualifies as "suspected" unexpected serious adverse reaction.

On behalf of the sponsor, Assign Safety Desk will be responsible to fulfil the requirements of expedited reporting of all SUSARs (suspected unexpected serious adverse reactions) to the Competent Authorities, Ethics Committees and principal investigators concerned according to national and European law and regulations.

For fatal and life-threatening SUSARs, this will be done no later than 7 calendar days after the sponsor or delegate is first aware of the reaction. Any additional relevant information to the initial report that was not available within the 7 calendar days will be reported within 8 additional calendar days. All other SUSARs will be reported within 15 calendar days.

Treatment codes will be unblinded for specific participants.

Principal investigators will be informed of all SUSARs related to the relevant IMP for all studies conducted with the same IMP, whether or not the event occurred in the current trial.

10.6 Reporting of Pregnancies

Women should not become pregnant during the treatment period of the study. If a subject becomes pregnant within the treatment period up to day 56, she should immediately inform the investigator about the pregnancy.

The investigator will complete a corresponding Pregnancy Report Form and send the form within 24 hours after becoming aware to Assign Safety Desk via fax or as pdf per e-mail:

Fax: PPD

Email: PPD

The first notification can be done via phone 24-hours Safety Hotline: PPD

Nevertheless, a written Pregnancy Report Form must be submitted for confirmation. The subject should attend follow-up visits as planned. In addition, subjects who become pregnant within the treatment period up to day 56 (and who received at least one dose) will be followed until the pregnancy outcome, even if this occurs after the study is completed.

Pregnancy itself is not regarded as an AE unless there is a suspicion that the IMP may have interfered with the effectiveness of a contraceptive medication. However, the outcome of all pregnancies that begin before day 56 (spontaneous miscarriage, elective termination, normal birth or congenital abnormality) will be followed up and documented even if the subject was discontinued from the study.

A pregnancy outcome of a congenital abnormality/birth defect would qualify as an SAE and will be reported to Assign Safety Desk for processing to the regulatory authority. A pregnancy outcome of an elective abortion without evidence of complications would not be processed as an AE.

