8.11.4 Pregnancy Test – Contraception

Pregnancy will be determined by evaluation of β-HCG in serum at screening, Visit 1, 3 and 5 (or at early termination) for all women.

A woman is considered of childbearing potential (WOCBP), i.e. fertile, following menarche and until becoming post-menopausal unless permanently sterile. Permanent sterilization methods include hysterectomy, bilateral salpingectomy and bilateral oophorectomy.

A postmenopausal state is defined as no menses for 12 months without an alternative medical cause. A high follicle stimulating hormone (FSH) level in the postmenopausal range may be used to confirm a post-menopausal state in women not using hormonal contraception or hormonal replacement therapy. However, in the absence of 12 months of amenorrhea, a single FSH measurement is insufficient.

Only females with a negative result will be allowed to receive study vaccinations.

Subjects with a positive pregnancy test will be excluded from further treatments and the Investigator will inform the CRO immediately by completing a pregnancy report from. Please see section 10.6.

After the last IMP use (Day 56) all subjects will be follow up until Day 365.

Contraception

Birth control methods which may be considered as highly effective are those that can achieve a failure rate of less than 1% per year when used consistently and correctly are considered as highly effective birth control methods. Such methods include:

_ combined (estrogen and progestogen containing) hormonal contraception associated with inhibition of ovulation:

- Oral
- Intravaginal
- transdermal

_ progestogen-only hormonal contraception associated with inhibition of ovulation:

- oral
- injectable
- implantable

_ intrauterine device (IUD)

_ intrauterine hormone-releasing system (IUS)

_ bilateral tubal occlusion

_ vasectomised partner

_ sexual abstinence

Acceptable birth control methods which may not be considered as highly effective are those that result in a failure rate of more than 1% per year include:

_ progestogen-only oral hormonal contraception, where inhibition of ovulation is not the primary mode of action

_ male or female condom with or without spermicide

_ cap, diaphragm or sponge with spermicide

Birth control methods which are considered unacceptable include:

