10.1.3 Serious Adverse Event (SAE)

A serious adverse event is any untoward medical occurrence that:

- results in death
- is life-threatening
- requires inpatient hospitalisation or prolongation of existing hospitalisation
- results in persistent or significant disability/incapacity
- consists of a congenital anomaly or birth defect

Other 'important medical events' may also be considered serious if they jeopardise the participant or require an intervention to prevent one of the above consequences.

The term "life-threatening" in the definition of "serious" refers to an event in which the participant was at risk of death at the time of the event. It does not refer to an event which hypothetically might have caused death if it were more severe.

Any pregnancy occurring during the clinical trial and the outcome of the pregnancy will be recorded and followed up for congenital abnormality or birth defect, at which point it would fall within the definition of "serious".

NOTE: to avoid confusion or misunderstanding of the difference between the terms "serious" and "severe", the following note of clarification is provided: "Severe" is used to describe the intensity of a specific adverse event, while "seriousness" is used for defining regulatory reporting obligations as supplied above.

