10.2 Recording of Adverse Events

All AEs occurring during the treatment period starting after the first vaccination at Visit 1 until termination of Visit 5 (day 56) observed by the investigator or reported by the subject (verbally or in the subject diary), will be recorded, whether or not related to the study treatment.

AEs will be requested at each visit during the treatment period up to Visit 5 (day 56) and additionally solicited by a subject's diary for 7 days after each vaccination. (see section 11.7)

The subjects will be asked generally (e.g. "How are you?") as well as specifically (e.g. "Have you experienced any problems since the last visit?").

The investigator must record all adverse events in the eCRF. One single adverse event page must be used per adverse event, from start to resolution, stating the following information: AE description, date of onset and end date, severity, relatedness, seriousness and action taken. Please consider definitions of section 10.1. Follow-up information should be provided as necessary.

If possible, the investigator should record the diagnosis. If a diagnosis is not available, the investigator should record each sign and symptom as individual adverse events. However, as soon as a diagnosis becomes available, all signs and symptoms should be summarised and replaced by the underlying adverse event term (e.g. common cold instead of separate AEs for headache, rhinorrhoea, arthralgia, fever etc.)

The AE should be documented stating the highest severity (i.e. if an AE goes from mild severity to moderate severity or vice versa, the whole episode of the AE should be reported with the moderate severity). Please consider Table 5 and 6 for grading local injection site reactions and systemic reactions.

For causality reporting purposes, the categories "definitely", "probably" and "possibly" qualify an event as "suspected" adverse reaction. AEs with missing causality assessment will be regarded as possibly related unless further specified.

Any medical condition that is present at screening will be considered as medical history and not reported as an AE. However, if the subject's condition deteriorates at any time during the study, it will be recorded as an AE.

It will be left to the investigator's clinical judgment to decide whether an AE requires the subject's removal from the study. In case of discontinuation, the subject will undergo an early termination visit.

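### The protocol undertakes to follow pregnancies but schedules no test or pregnancy question after Visit 5, so some late conceptions within its own scope depend on self-report alone

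*Combined protocol and SAP*

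**What the plan says.** Two protocol sections set the scope of pregnancy follow-up, and they differ.

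- Section 10.1.3, among the safety definitions: "Any pregnancy occurring during the clinical trial and the outcome of the pregnancy will be recorded and followed up for congenital abnormality". No date limit is given, and the synopsis sets study duration at 12 months per subject.
- Section 10.6, the reporting section: "If a subject becomes pregnant within the treatment period up to day 56, she should immediately inform the investigator about the pregnancy". Women who conceive in that period and have had at least one dose "will be followed until the pregnancy outcome, even if this occurs after the study is completed". The outcome duty is restated for "the outcome of all pregnancies that begin before day 56".

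Once a pregnancy is known, the route is clear. The investigator completes a Pregnancy Report Form and must "send the form within 24 hours after becoming aware". A congenital abnormality "would qualify as an SAE and will be reported to Assign Safety Desk for processing to the regulatory authority", and that sentence carries no date limit.

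On detection, section 8.11.4 says: "Pregnancy will be determined by evaluation of β-HCG in serum at screening, Visit 1, 3 and 5". It adds early termination as a further occasion. Section 8.5.5, Table 3 and the SAP schedule (1.6) also place the last test for completers at Visit 5. Sections 8.6.1 and 8.6.2 list only blood sampling for antibodies, plus passive-transfer serum at Visit 7. Note 3 to Table 2 says that adverse events are not recorded at those two visits.

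**The concern.** MV-CHIK is a live recombinant virus, and the protocol has itself chosen to follow pregnancies for congenital abnormality. That undertaking works only if the pregnancies are found. After Visit 5, nothing scheduled looks for them.

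This leaves two gaps. Inside 10.6's own period, a conception close to or after the last test is covered, but nothing scheduled will reveal it. Beyond day 56, only 10.1.3 applies, and it comes with no procedure for finding a pregnancy. What is at stake is the completeness of a safety commitment. The PRNT₅₀ analysis and the other endpoints are not touched.

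**Working it through.** The documents give no figure for this, so the check is a comparison of schedules followed by day counts.

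**Is anything scheduled after Visit 5?**

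- *Table 2.* In the protocol text as extracted, the third on-study pregnancy-test mark appears under Visit 6. The vital signs, examination and laboratory rows are displaced the same way, while the protocol text and the SAP schedule say Visit 5. I read this as a table-extraction shift, not a Visit 6 test.
- *Section 9.10.2.* Subjects are asked about medication and vaccinations at each visit. That is contact with staff, but not a pregnancy question.
- *Early termination after Visit 5.* Section 8.11.4 and the early-termination column of the SAP schedule indicate a test. Section 8.7 and note 7 to the schedule send these women to the Visit 7 procedures, which include none. The plan is unclear here.

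**Undetected conception days within 10.6's scope**

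Inputs:
- End of scope: day 56 (10.6).
- Visit 5: day 51 to 61 (8.5.5).
- Lag L from conception to a positive serum β-HCG: 0 as a floor, and 7 to 14 days as an assumption.

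Formula: undetected days = max(0, 56 − (Visit 5 day − L)).

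| Visit 5 | L = 0 | L = 7 | L = 14 |
|---|---|---|---|
| Day 51 | 56 − 51 = 5 | 56 − 44 = 12 | 56 − 37 = 19 |
| Day 56 | 0 | 56 − 49 = 7 | 56 − 42 = 14 |
| Day 61 | 0 | 56 − 54 = 2 | 56 − 47 = 9 |

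The 5 days in the L = 0 column are days 52 to 56, and they need no assumption about the assay. These counts include day 56. On 10.6's other wording, which requires a start before day 56, each non-zero count falls by one.

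**Beyond day 56**

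Nominally 365 − 56 = 309 days remain from Visit 5 to Visit 7. Within the visit windows this is 351 − 61 = 290 to 379 − 51 = 328. Section 10.1.3 applies throughout, with no scheduled detection for completers.

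**Would a question at Visit 6 be enough?**

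With Visit 5 on day 56 and L = 14, the window is days 43 to 56. At a day-182 Visit 6 these conceptions are 182 − 56 = 126 to 182 − 43 = 139 days old. Across the visit windows the earliest undetected day is 38 (Visit 5 on day 51, L = 14), so the range is 168 − 56 = 112 to 196 − 38 = 158 days. A woman should know by then. A question also picks up a pregnancy that has already ended, which a test at Visit 6 could miss. Asking about the time since Visit 3 (day 33 at the latest) covers the whole window.

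**How many events?**

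As an illustration, assume 30 women and contraceptive failure of 1% to 10% per year. Section 8.11.4 gives only below 1% for highly effective methods and above 1% for others. At nominal timing, expected conceptions in the window for the whole trial run from 30 × 0.01 × 7/365 = 0.006 to 30 × 0.10 × 14/365 = 0.12.

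**The case against.** The best defence is that the plan already does a good deal. Contraception is required for the entire study (inclusion criterion 5). Women are tested at screening, before each dose and at Visit 5, and 10.6 tells them to report at once. Expected events are well below one. Section 10.1.3 is a definition that explains when a pregnancy outcome becomes serious, whereas 10.6 is the operative section. The consent pages were removed before review and the eCRF is not shown, so what women are told about late pregnancies cannot be judged. The documents also give no risk period after vaccination from which to argue that surveillance is too short.

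Most of this stands, and it fixes the weight at minor. It does not remove the gap: the scheduled visits contain no prompt, and 10.6 covers conceptions that its last test cannot show.

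A reader might infer more than the documents support:

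- *That 10.1.3 and 10.6 contradict each other.* Staff can obey both. The scopes differ, and the wider one has no procedure behind it.
- *That birth defects would go unreported.* A known one has a reporting route with no date limit. The gap is in finding the pregnancy.
- *That the blind window is always 7 to 14 days.* The lag is an outside assumption. A constant window follows only if the period is taken to end at Visit 5, whereas 10.6 names day 56.
- *That a large share of pregnancies would be missed.* The 7 to 14 days at nominal timing are 12.5% to 25% of 56 calendar days. They are not a share of pregnancies, and self-report will find some of them.

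**Conclusion.** The point holds as a minor gap in safety follow-up. For completers, no pregnancy test or question is scheduled after Visit 5, although 10.6 covers conceptions up to day 56 and 10.1.3 covers the whole trial. With Visit 5 on days 51 to 55, up to 5 in-scope conception days follow the last test on the documents alone. With an assumed lag of 7 to 14 days, the undetected window is 2 to 19 days, depending on when Visit 5 falls. A further 309 nominal days lie within 10.1.3 only.

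This rests on reading the Visit 6 mark in Table 2 as an extraction shift and, for every figure except the 5 and the 309, on the assumed lag. Few events are expected, and no endpoint or analysis changes.

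**What to change.** 1. At Visit 6, and at any early termination visit after Visit 5, ask each woman in every group whether a pregnancy has begun since Visit 3, and record the estimated conception date. Report any through the existing Pregnancy Report Form, with 10.6's follow-up to outcome.
2. Give 10.1.3 and 10.6 one stated scope. There are two options:
   - *The whole trial,* as 10.1.3 now says. The question is then repeated at Visit 7.
   - *An explicit limit no narrower than 10.6:* the latest of day 56, Visit 5, or 28 days after the last injection (MV-CHIK or placebo). A second injection on day 23 gives 23 + 28 = 51, and no second injection gives 0 + 28 = 28, so day 56 or Visit 5 governs. A second injection on day 33 gives 61. With Visit 5 in its window, the limit falls on day 56 to 61 for every woman. This narrows 10.1.3, and the amendment should say so.
3. Editorially, 8.11.4 dates the last use of study product to day 56. The last injection is at Visit 3 (day 28 ±5).

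The cost is one or two eCRF items at visits already attended, a protocol amendment under 16.1, and possibly a few more pregnancies to follow. No extra blood draw or visit is needed.

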10.7 Development Safety Update Reports

Assign Data Management and Biostatistics GmbH will submit a DSUR once a year throughout the clinical trial to the competent authority (MHRA), ethics committee, HRA (where required) and Host NHS trust according to applicable regulations and requirements.

11. ASSESSMENT OF SAFETY

Adverse event rates compared between 5 different treatment groups will be used to evaluate the secondary study objective. Please also refer to Table 2, summarising study procedures including safety assessments.

11.1 Safety Laboratory Parameter Assessments

Haematology, blood chemistry, coagulation parameters and urinalysis will be assessed for subject's safety at screening, Visit 3, Visit 5 and additionally at Early Termination (if applicable). Please refer to section 8.11.1

11.2 Symptom-directed Physical Examination

A full physical exam will be performed at screening and a system based physical examination will be done, if necessary according to findings in a symptom-directed physical examination at Visit 1, 3 and 5. This means if a symptom is reported by the subject, a system-based assessment will be performed, if needed, for a detailed check of the affected body system.

Any symptom reported after first vaccination, including worsening of pre-existing conditions (i.e. medical history/concomitant diseases), will be recorded as AE.

11.3 System-based Physical Examination

All subjects will undergo a system-based physical examination, including but not limited to assessment of general appearance and skin, head/eyes/ears/nose/throat, respiratory system, cardiovascular system, abdominal and gastrointestinal system, musculoskeletal system, neurological system and lymph nodes.

This system-based physical examination will only be performed if necessary according to findings of the symptom-directed physical exam at Visit 1, 3 and 5.

11.4 Vital Signs and Body Temperature

Systolic and diastolic blood pressure and pulse rate as well as body temperature will be recorded at screening and Visit 1, 3 and 5 with the subject at rest in a sitting position.

11.5 Post Vaccination Reactogenicity Assessments

All subjects enrolled in the study and who receive at least one study treatment (MV-CHIK or placebo) will be followed up 28 days after each study treatment. Solicited and unsolicited AEs will be recorded at each visit until the end of the treatment phase at Visit 5.

11.6 Local and Systemic Tolerability

The local tolerability (i.e. injection site reactions) will be inspected and evaluated by the investigator two hours after each IMP administration.

Additionally, local tolerability (i.e. inspection of the previous injection site) will be assessed at the following visits and prior to application of the subsequent vaccination at Visit 3 (day 28). Furthermore, local tolerability will be evaluated by the subjects in the subject diaries for 7 days starting 6 hours after each treatment.

The grading of local reaction will be performed by means of a stencil (provided to the subject as shown in Appendix 1) and per "Guidance for Industry: Toxicity Grading Scale for Healthy Adult and Adolescent Volunteers Enrolled in Preventive Vaccine Clinical Trials", modified, reflecting the guidance of the Brighton Collaboration (Table 5).

Findings in the local tolerability examination by the investigator as well as local tolerability findings recorded in the subject diary will be covered as adverse events in the eCRF.

11.7 Subject Diary

The subjects will be instructed to complete a diary for 7 days after each vaccination to document local and systemic tolerability as well as body temperature.

Solicited local and solicited systemic AEs will be assessed by the subjects themselves by checking for presence of the listed symptoms and measuring the size of the affected area where appropriate (a template will be provided for local reaction grading, as shown in Appendix 1). The diary will also provide space for recording unsolicited AEs and concomitant medication.

Recording should be done approximately at the same time each day, starting on the day of vaccination. The first entry should be made 6 hours ± 1 h after vaccination at Visit 1 and Visit 3.

The subjects' diaries will be collected and verified for completeness by the investigator at Visit 2 and Visit 4. Any AE recorded in the subject diaries will be entered in the eCRF by the investigator or authorised delegates. The investigator will re-evaluate the severity of the reported local and systemic AEs according to the below Tables 5 and 6.

Diary solicited systemic AEs include: nausea, vomiting, headache and fatigue, also to be documented in the eCRF.

In addition, body temperature will be recorded daily for 7 days and fever will be graded by the investigator according to the FDA Guidance for Industry. For details see below Table 6.

Table 5: Grading of Local Reactions

Local reaction to injectable product	Mild (grade 1)	Moderate (grade 2)	Severe (grade 3)	Potentially life threatening (grade 4)
Pain	Does not interfere with activity	Interfere with activity or repeated use of non-narcotic pain reliever	Prevents daily activity or repeated use of non-narcotic pain reliever	Emergency room (ER) visit or hospitalisation
Tenderness	Mild pain to touch	Pain with movement	Significant pain at rest	ER visit or hospitalisation
Erythema/ Redness¹	≤ 5 cm	5.1–10 cm	> 10 cm	Necrosis or exfoliate dermatitis
Swelling²	≤ 5 cm and does not interfere with activity	5.1–10 cm or interfere with activity	> 10 cm or prevents daily activity	Necrosis
Itching	Does not interfere with activity	Interferes with activity or repeated use of non-narcotic pain reliever	Prevents daily activity or repeated use of anti-inflammation and pain-relieving ointment	Emergency room (ER) visit or hospitalisation
Induration¹	≤ 1 cm Does not interfere with activity	> 1 to < 3 cm Interferes with activity or repeated use of non-narcotic pain reliever	≥ 3 cm Prevents daily activity or repeated use of anti-inflammation and pain-relieving ointment	Not applicable

¹ In addition to grading the measured local reaction at the greatest single diameter, the measurement should be recorded as a continuous variable.

² Swelling should be evaluated and graded using the functional scale as well as the actual measurement.

Table 6: Grading of Systemic Reactions

Systemic Reaction (General)	Mild (grade 1)	Moderate (grade 2)	Severe (grade 3)	Potentially life threatening (grade 4)
Nausea/ vomiting	No interference with activity or 1-2 episodes/ 24 hours	Some interference with activity or >2 episodes/ 24 hours	Prevents daily activity, requires outpatient IV hydration	Emergency room (ER) visit or hospitalisation for hypotensive shock
Diarrhoea	2-3 loose stools or < 400 gms/ 24hours	4-5 stools or < 400-800 gms/ 24hours	6 or more watery stools or >800 gms/ 24 hours or requires outpatient IV hydration	ER visit or hospitalisation
Headache	No interference with activity	Repeated use of non-narcotic pain reliever >24 hours or some interference with activity	Significant; any use of narcotic pain reliever or prevents daily activity	ER visit or hospitalisation
Fatigue	No interference with activity	Some interference with activity	Significant; prevents daily activity	ER visit or hospitalisation
Myalgia	No interference with activity	Some interference with activity	Significant; prevents daily activity	ER visit or hospitalisation
Illness or clinical AE (as defined according to applicable regulations)	No interference with activity	Some interference with activity not requiring medical intervention	Prevents daily activity and requires medical intervention	ER visit or hospitalisation
Fever (°C)	38.0 - 38.4	38.5 - 38.9	39.0 - 40.0	>40.0

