Special attention was directed to any occurrence of joint pain during the MV-CHIK study due to significant joint pathology caused by CHIKV. The subjects were asked to report any symptoms of joint pain in their subject diary and they were asked for any symptoms during each visit. Overall, 23.8% (10/42) of the subjects reported any signs of joint pain or arthralgia during the treatment period, 11.9% (5/42) of which were rated as related to the study treatment. In all 5 cases the joint pain was described as transient musculoskeletal pain, which was accompanied by flu like symptoms. Pain in the limbs associated with MV-CHIK injection was largely graded as mild (82%), was self-limiting and did not engender any withdrawals from the study. The rate of musculoskeletal pain decreased from 12% (n=5; 67% mild) at the first visit to 2% (n=1; 100% mild) at visit 5. No signs of inflammation were observed.

Severe and serious AEs occurred only for subjects treated with MV-CHIK. All serious AEs reported were non-local and unsolicited. Overall, seven severe AEs occurred (in six participants), of which five were solicited and related to vaccination including headache, local erythema, local induration, local pain and pyrexia.

The number of overall AEs and related AEs increased with the MV-CHIK dose. In addition, local reactions to MV-CHIK vaccination increased dose-dependently and were deemed related to the high inoculation volume (1mL) together with the formulation's salt buffer content.

The evaluation of safety laboratory parameters (haematology, serum chemistry, urinalysis) did not indicate any safety issues. There were no clinically relevant abnormalities observed in haematology, clinical chemistry, coagulation or urinalysis laboratory parameters.

The Clinical Study Report has been finalised in Q4/2014. The study results were published in Ramsauer et. al. Lancet Infect Dis 2015.

MV-CHIK-203:

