4.6 Benefit/Risk Assessment

General

Potential risks that are frequently associated with vaccination are the occurrence of local reactions such as oedema, induration and erythema, transient local pain or tenderness at the injection site as well as mild to moderate headache, myalgia, flu-like symptoms or fatigue. Vaccines have been known to induce allergic and anaphylactic reactions apart from reactions at the vaccination site and systemic flu-like reactions. Additionally, needle picks for blood sampling may cause discomforts and local reactions.

MV-CHIK Related

As described above, adverse events (AEs) previously reported with MV-CHIK include injection site pain, headache, fatigue, and joint pain or arthralgia. Refer to the current version of the Investigators' Brochure for more detail.

Potential for Severe Adverse Reaction

In the past, a live virus vaccine against Chikungunya virus, which was based on an attenuated Chikungunya-strain was associated with mild, transient arthralgia in immunised individuals. The MV-CHIK vaccine is based on live measles virus and contains no live Chikungunya virus. Therefore, induction of chikungunya-like symptoms is not expected. However, the subjects will be monitored for occurrence of arthralgia, an adverse event of special interest (AESI).

Potential Benefit

If the clinical development of MV-CHIK is successful, the potential benefit of MV-CHIK vaccination would be life-long protection against Chikungunya infection helping people, who are at risk of acquiring a possibly life-threatening infection with CHIKV.

A boost in measles immunity may be an additional benefit.

Conclusion

The benefit risk ratio is considered favourable.

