8.9 Discontinuation/Withdrawal of Subjects

Subjects may withdraw from participation in the study at any time. If a subject withdraws or is withdrawn prior to completion of the study, the reason for this decision should be recorded in the electronic case report forms (eCRFs) although it is recognised that the subject may refuse to provide a reason.

Generally, any enrolled/vaccinated subject may withdraw or be withdrawn from the study for the following reasons:

- The subject withdraws consent
- The subject fails to comply with the requirements of the protocol
- At the discretion of the investigator
- For an adverse event, which at the discretion of the investigator requires discontinuation of the subject or results in inability to continue to comply with trial procedures
- if the administration of a drug, which is not permitted by the study protocol, becomes necessary (this should be discussed and agreed between the investigator and the sponsor)
- violation of exclusion criteria 1, 4, 5, 7, 12, 15, 16, 17, 18, 19 or 20 during the study (this should be discussed and agreed between the investigator and the sponsor)

All subjects who withdraw or are withdrawn prematurely from the study will undergo an early termination visit (see section 8.7).

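### Arthralgia is the adverse event of special interest, but it is not a named diary symptom, can be absorbed into a diagnosis and has no dedicated analysis, so its rate is likely to be understated

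*Combined protocol and SAP*

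**What the plan says.** - **Status of arthralgia.** Protocol 4.6 states that "the subjects will be monitored for occurrence of arthralgia, an adverse event of special interest (AESI"). Protocol 10.1, which defines the safety terms, contains no AESI definition.
- **Diary.** Protocol 11.7 states: "Diary solicited systemic AEs include: nausea, vomiting, headache and fatigue, also to be documented in the eCRF". Body temperature is recorded as well. There is also a free-text route: "The diary will also provide space for recording unsolicited AEs and concomitant medication". The diary runs for 7 days after each injection.
- **Grading.** Table 6 has rows for diarrhoea and myalgia, which the diary sentence does not name. It has none for arthralgia, only a general row headed "Illness or clinical AE (as defined according to applicable regulations").
- **Visits.** Protocol 10.2 states: "AEs will be requested at each visit during the treatment period up to Visit 5 (day 56"). Its sample questions are general, and none mentions joints.
- **Replacement by diagnosis.** Under 10.2, once a diagnosis is available the separate signs and symptoms give way to it: "e.g. common cold instead of separate AEs for headache, rhinorrhoea, arthralgia, fever etc".
- **Analysis.** SAP 6.2.1 and 7.1 list adverse event overviews, solicited events by symptom, and unsolicited events by system organ class and preferred term (Table 1.4.13, with related, severe, serious and medically attended versions in 1.4.14 to 1.4.20). No table or listing is devoted to an AESI.
- **Phase I.** Protocol 4.4.1 reports that subjects were asked about joint pain in the diary and at each visit. On the five related cases it says: "In all 5 cases the joint pain was described as transient musculoskeletal pain, which was accompanied by flu like symptoms".

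**The concern.** Joint symptoms are the one safety question specific to this vaccine, because of the joint pathology that Chikungunya virus causes. After 4.6 promises to monitor them, no later section says how. Three steps each lean towards a lower count: subjects are not prompted for joint pain by name, a reported joint pain may be folded into a broader diagnosis, and no analysis brings joint reports together.

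This matters more here than in earlier trials. Protocol 4.4.1 says that adverse events increased with dose in phase I. Groups D and E receive 1×10^6 TCID50, above the 5×10^5 upper end that Protocol 4.5 gives for earlier trials. If a lower arthralgia rate were seen at this dose, it could not be told apart from the effect of asking less.

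**Working it through.** **1. Reproduce the documented phase I rates (Protocol 4.4.1).**
- Any joint pain or arthralgia: 10/42 = 23.8% (exact 95% CI 12.1% to 39.5%).
- Related: 5/42 = 11.9% (exact 95% CI 4.0% to 25.6%).

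Both percentages match the protocol. The confidence intervals are added here.

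**2. Compare how joint pain is sought.**

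| Feature | Phase I (4.4.1) | This trial (10.2, 11.7) |
|---|---|---|
| Diary | joint pain asked for; two weeks | joint pain not among the named terms; 7 days |
| Visits | asked about joint pain at each visit | general questions |
| Reported as | among the solicited events (23.8%) | would fall under unsolicited events |
| Injections | up to day 90 | day 0 and day 28; events recorded to day 56 |
| Denominator | 42, including the Priorix controls | 60, all given MV-CHIK at least once |

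The two rates would not be like for like, whatever the true risk.

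**3. Effect of the replacement rule, applied to the phase I cases.** All five related cases came with flu-like symptoms, the picture most open to a single diagnosis. Let k be the number absorbed. The documents do not give k, so 0 to 5 is an assumed range. The any rate is (10 − k)/42 and the related rate is (5 − k)/42.

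| k | Any arthralgia | Related arthralgia |
|---|---|---|
| 0 | 10/42 = 23.8% | 5/42 = 11.9% |
| 3 | 7/42 = 16.7% | 2/42 = 4.8% |
| 5 | 5/42 = 11.9% | 0/42 = 0% |

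**4. What this trial might see.** Assume that the phase I rates carry over.
- Expected in 60: 60 × 10/42 = 14.3 with any arthralgia and 60 × 5/42 = 7.1 with related arthralgia.
- Expected in a group of 12: 2.9 and 1.4.
- Chance of at least one case in a group of 12, from 1 − (1 − p)^12: 0.962 for any and 0.782 for related.
- If only half the cases were captured (assumed), p becomes 5/42 and 2.5/42, and these chances fall to 0.782 and 0.521.

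**5. Check the replacement rule against the rest of the plan.** The example in 10.2 also names headache and fever. Headache is a named diary symptom that 11.7 wants in the eCRF, and fever is graded from the diary temperature. SAP Tables 1.4.8 to 1.4.12 count solicited events by symptom and severity. Neither document says whether a diary-reported headache stays in those tables once a common cold is diagnosed.

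**The case against.** The other side has real points, and several stand.

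- **A reader might infer that no table would show arthralgia.** That is wrong. Arthralgia kept as its own event is a preferred-term row in Table 1.4.13 and, where it applies, in Tables 1.4.14 to 1.4.20. The listings give its dates, severity, causality and group, so groups can be compared. What is missing is a summary that pools joint reports.
- **A reader might infer that the diary certainly omits it.** The verb in 11.7 is open-ended and the diary form is not in the documents. Protocol 4.4.1 introduces its phase I solicited events with a similarly open list that omits arthralgia, then reports arthralgia among them. Omission is the natural reading, not a proven one. Still, an AESI should not rest on an item that the protocol leaves unstated.
- **A reader might infer that any diagnosis erases the event.** Replacement applies only when a diagnosis becomes available, so isolated arthralgia stays. The diaries are kept as source data. Phase I reported influenza-like illness (45.2%) and arthralgia (23.8%) side by side. A fall from 5/42 to 0/42 is therefore an assumed worst case.
- **Other routes exist.** These are free text in the diary, enquiry at every visit to day 56, and the general grading row and severity scale. They reduce the loss, but none prompts for joint pain.
- **Visits 6 and 7.** Adverse events are not recorded there because subjects may by then be in other studies. That reason is stated and sensible, and this point does not ask for a change.
- **Precision.** A recorded 0/12 has an exact upper 95% limit of 26.5%, but that holds for any event with no cases, so it does not measure this defect. The plan reports no confidence intervals for adverse event rates.

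**Conclusion.** The concern holds as a gap between what 4.6 promises and what the rest of the plan provides. Arthralgia is not a named solicited term, has no grading row, is a listed example in the replacement rule, and has no dedicated analysis. Understatement is the likely direction, and comparison with phase I would be unsound. The documents do not support saying that the rate will certainly be understated, or by how much. Across the assumed range, the related rate in the phase I data would read anywhere from 11.9% down to 0%, and the any rate from 23.8% down to 11.9%. The projections to 60 subjects rest on carrying over a phase I rate whose 42 subjects include controls and whose diary ran two weeks.

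There is also a narrower wording problem. Exclusion criterion 7 concerns moderate or severe arthritis or arthralgia before screening, yet Protocol 8.9 permits withdrawal for "violation of exclusion criteria 1, 4, 5, 7, 12, 15, 16, 17, 18, 19 or 20 during the study". Protocol 17.1 says that subjects who develop exclusion criteria will be withdrawn unless the sponsor approves an exception. Protocol 8.9.1 describes stopping vaccination while follow-up continues, unless the subject is explicitly withdrawn. It is tempting to conclude that AESI cases will be lost to follow-up, but the discretion in 8.9 and the exceptions in 17.1 do not support that. The passages only need to be reconciled.

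**What to change.** 1. **Protocol 11.7:** name joint pain/arthralgia, and myalgia (already graded in Table 6), in the diary's solicited list. Add an arthralgia row to Table 6.
2. **Protocol 10.2:** add a direct question on joint pain at each visit to day 56. State that the AESI and all solicited symptoms are recorded alongside any diagnosis and linked to it, not replaced by it.
3. **SAP 6.2 and 7:** add one table and one listing of arthralgia by treatment group, severity and relatedness, with n, % and exact 95% confidence intervals.
4. **Protocol 8.9, 8.9.1 and 17.1:** reconcile what happens when a subject meets exclusion criterion 7 during the study.

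The cost is a few diary lines, a revised eCRF completion rule, one grading row and one table with its listing. The downside is that the reported arthralgia rate will be higher than under the present wording, and the report should explain that this reflects active enquiry. Differences from phase I in diary length, injection schedule and control subjects will remain, so any comparison still needs that caveat.
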